8.17 Adverse Events

Each patient must be carefully monitored for adverse events – this includes clinical laboratory test variables. At each evaluation, the investigator will determine whether any adverse events have occurred. The patient will be questioned in a general manner and no specific symptoms will be suggested during the questioning. If any adverse events have occurred, they will be recorded on the adverse event pages of the CRF. If known, the diagnosis should be recorded in preference to the listing of individual signs and symptoms. An assessment must be made of the seriousness, intensity, and relationship to the administration of the study medication.

8.17.1 Definition of Adverse Events

Adverse Event

Any undesirable event occurring to a patient during a clinical trial, whether considered related to the investigational product or not.

Worsening of the Condition Being Investigated or of Concurrent Conditions

The worsening or exacerbation of any concurrent illness or condition will be considered an adverse event. If the symptoms of the condition being treated with study medication worsen after the start of administration of drug, these symptoms will be considered adverse events if, in the investigator's opinion, their occurrence or severity is outside of what is expected.

Relationship to investigational product:

The assessment of the relationship of an adverse event to the administration of study drug (none, unlikely (remote), possible, probable, not assessable) is a clinical decision based on all available information at the time of the completion of the case report form.

None - includes: (1) the existence of a clear alternative explanation (e.g. mechanical bleeding at surgical site); or (2) non-plausibility (e.g., the patient is struck by an automobile at least where there is no indication that the drug caused disorientation that may have led to the event; cancer developing a few days after drug administration).

Unlikely (remote) - a clinical event, including a laboratory abnormality, with an improbable time sequence to drug administration and in which other drugs, chemicals or underlying disease provide plausible explanation.

Possible - a clinical event, including a laboratory abnormality, with a reasonable time sequence to administration of the drug, which could also be explained by concurrent disease* or other drugs or chemicals. Information on drug withdrawal may be lacking or unclear.

Probable - a clinical event including a laboratory abnormality, with a reasonable time sequence to administration of the drug, unlikely to be attributed to concurrent disease* or other drugs or chemicals, and which follows a clinically reasonable response on withdrawal (dechallenge).

Not assessable - a report of an adverse event which cannot be judged because information is insufficient or contradictory, and which cannot be supplemented or verified.

* Concurrent disease includes concomitant, intercurrent and underlying disease/condition. Concomitant disease - any other illness the subject may have at

the time of entering the clinical trial. Intercurrent disease - any other illness the subject may develop during the clinical trial. Underlying disease - the illness which is the indication for study drug therapy.

Factors to be considered include:

- The temporal sequence from drug administration (The event should occur after the drug is given. The length of time from drug exposure to event should be evaluated in the clinical context of the event.)
- Recovery on discontinuation (dechallenge), recurrence on reintroduction (rechallenge) (Subject's response after drug discontinuation (dechallenge) or subjects response after drug re-introduction (rechallenge) should be considered in the view of the usual clinical course of the event in question.)
- Underlying, concomitant, intercurrent diseases (Each report should be evaluated in the context of the natural history and course of the disease being treated and any other disease the subject may have.)
- Concomitant medication or treatment (The other drugs the subject is taking or the treatment the subject receives should be examined to determine whether any of them may be recognized to cause the event in question.)
- Known response pattern for this class of drug (Clinical/preclinical.)
- Exposure to physical and/or mental stresses (The exposure to stress might induce adverse changes in the recipient and provide a logical and better explanation for the event.)
- Pharmacology and pharmacokinetics of the test drug (The pharmacokinetic
 properties (absorption, distribution, metabolism and excretion) of the test drug (s)
 the subject is taking, coupled with the individual subject 's pharmacodynamics
 should be considered.)

Intensity (Severity) of the Event

In addition to assessing the connection with administration of the investigational drug, the intensity (severity) of each adverse event must be assessed. The following classification should be used:

- Mild usually transient in nature and generally not interfering with normal activities
- Moderate sufficiently discomforting to interfere with normal activities.
- Severe prevents normal activities.

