5 OVERALL STUDY DESIGN AND PROCEDURES

5.1 Study Design

This study will be conducted as a randomized, double-blind, placebo-controlled, outpatient, parallel group study in adult patients with recent onset type 1 diabetes. Patients will be randomly assigned to treatment with either atorvastatin or placebo in a one-to-one manner. The treatment phase will be 18 months for each patient. Patients who are withdrawn from the study during the first nine months of the treatment phase will be replaced. A maximum of 160 patients will complete all study procedures. The number of subjects included may be adjusted following an interim analysis as specified in section 9.9)

Starting dose will be 40 mg per day of atorvastatin or a matching number of placebo tablets. After a run-in period of 4 weeks the daily dose will be increased to 80 mg per day or matching placebo. In case of side effects (e.g. myalgia) the dose will be reduced to 40 mg per day by the discretion of the investigator.

Efficacy on beta-cell preservation will be assessed by means of two-hour mixed-meal tolerance tests at baseline and after 12 months and 18 months of treatment. Safety data and data on metabolic control will be obtained at baseline and after 3, 6, 12 and 18 months of treatment.

Patients should continue insulin treatment throughout the study. A tight glycemic control should be aimed (Target HbA1c ≤ 6.5 %) from Visit 2 on.

5.2 **Study Flow Chart**

Visit	Screening	Visit 1 *	Visit 2	Visit 3	Visit 4	Visit 5	Early Discontinuation
Time	-28 to -2 days	0	3 months (±2 weeks)	6 months (± 10 days)	12 months (± 2 weeks)	18 months (± 2 weeks)	
Informed consent	х						
Inclusion/Exclusion Criteria	х						
Randomization		X					
Demographic Data	х						
Medical History and concomitant Illnesses	х						
2 h MMTT		X			х	х	
12 lead ECG	х					х	х
Vital signs	х	X	х	x	x	х	х
Body height ¹ , weight and BMI		х	х	х	х	х	х
Physical examination	х					х	x
Adverse Events		х	х	X	х	х	х
Concomitant Medication	х	х	х	х	х	х	х
Documentation of Insulin dose	Х	Х	х	х	х	х	х
Drug accountability		X	х	x	x	х	x
Hematology	х	х	х	х	х	х	х
Clinical Chemistry ¹	х	х	х	х	х	х	х
Serum Lipids	х	х	х	х	х	х	х
Coagulation	Х						
Urinalysis	х						
Transcriptional studies		х	х				
Cytokines/chemokines		Х	х		х	х	
Beta cell autoantibodies	х			х	х	х	
HCG ²	х	Х	х	х	х	х	х
Plasma CRP		х	х		х	х	
HbA1c	х	х		х	х	х	х
Fasting C-peptide		X³			X ³	X³	

Visit 1 only ²only female patients ³ sampled during mixed meal tolerance test

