8.3 Concomitant Medication, including insulin requirements

Details on Concomitant Medication will be obtained at Screening Visit and all subsequent visits, including start date and stop date, frequency, and route of application.

Insulin treatment should be continued throughout the study with a recommended treatment goal of HbA1c below 6.5% from Visit 2 on.

However, missing this treatment goal will not be a reason for discontinuing a patient from further participation.

It is of uttermost importance, that the start date of insulin therapy is obtained and the current insulin dose is thoroughly documented at each visit.

The current insulin dose (the daily dose of all sorts of insulin) will be summed up and the weight-corrected insulin requirements will be calculated (expressed as IU per kg).

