9.6 Safety Evaluation

All randomized patients who take at least one dose of study medication will be included in the safety analysis. The incidence of adverse events, drug-related adverse events and premature discontinuations will be summarized descriptively for each treatment group. The incidence of treatment emergent ECG-findings and of abnormally high and low laboratory values will be presented by treatment group. Descriptive statistics for changes from baseline in vital signs and laboratory values will be presented by treatment group.

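### Section 8.17.1 leaves worsening diabetes symptoms to an undefined investigator expectation, and under a 6.5% HbA1c target the protocol neither classifies nor systematically collects severe hypoglycaemia and ketoacidosis

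*Protocol*

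**What the plan says.** **Target.** Section 5.1 states: "A tight glycemic control should be aimed (Target HbA1c ≤ 6.5 %) from Visit 2 on". Section 8.3 calls it a "recommended treatment goal of HbA1c below 6.5% from Visit 2 on" and adds that missing it is no reason to discontinue a patient. The two sections differ on whether 6.5% itself meets the target and should be reconciled, but nothing here depends on that.

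**Definition.** Section 8.17.1 contains three statements in sequence:
- The general definition of an adverse event is "Any undesirable event occurring to a patient during a clinical trial, whether considered related to the investigational product or not".
- For concurrent conditions, "The worsening or exacerbation of any concurrent illness or condition will be considered an adverse event".
- For the condition being treated with study medication, symptoms that worsen after the start of treatment count only if, in the investigator's opinion, "their occurrence or severity is outside of what is expected".

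**Questioning.** Section 8.17 states: "The patient will be questioned in a general manner and no specific symptoms will be suggested during the questioning". Section 5.3.2.1, however, requires three specific muscle questions at the Day 28 telephone contact.

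**What is not there.** The protocol text does not mention hypoglycaemia. Ketoacidosis appears once, as a medical-history item at screening (Section 8.2). The flow chart in Section 5.2 has no on-study item for either.

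**The concern.** Every patient is on insulin and is steered toward a tight HbA1c target, so low-glucose episodes and metabolic decompensation are foreseeable during the trial. The protocol does not say which of the statements in 8.17.1 governs them. One investigator may record an episode as an undesirable event. Another may regard it as part of the disease, and expected, and leave it out. Both would be following the text.

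General questioning adds to this, because a patient may not volunteer an episode that happened months before the visit.

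Two things are at stake: the completeness of the descriptive safety comparison, and the context for reading HbA1c and insulin dose. Because this concerns what is collected, a later analysis plan cannot repair it. An episode that was never written down cannot be tabulated.

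**Working it through.** The protocol states no rate of hypoglycaemia or ketoacidosis, and none of its figures rests on this rule, so there is no figure to reproduce. The check is to take each kind of episode through the stated rules.

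**1. Which rule applies?**
- *Episode leading to hospitalisation or immediately life-threatening.* Section 8.17.2 applies to any untoward medical occurrence meeting its criteria and has no expectedness test. These episodes are covered.
- *Severe hypoglycaemia managed outside hospital with another person's help.* Low glucose under insulin is most naturally an effect of insulin, not a worsening symptom of diabetes. On that reading it falls under the general definition and is an adverse event without any filter, but the protocol does not say so. Section 8.17.2 names convulsions without admission as an example of an important medical event. Otherwise, seriousness here is left to medical judgment. The classification is unsettled.
- *Non-serious decompensation, such as symptomatic hyperglycaemia or ketosis.* This is a worsening of symptoms of the treated condition, so the filter applies directly. Whether it is recorded depends on what each investigator expects.

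A note to the causality categories in 8.17.1 counts the underlying disease, meaning the indication for study drug, as a concurrent disease. If that meaning is carried over to the sentence on concurrent conditions, worsening diabetes is always an adverse event under one sentence and only conditionally so under the next. The note is attached to causality, so this adds to the ambiguity but does not settle it.

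**2. Would another procedure pick the episode up?**
- The clinical chemistry list in 8.8.2 contains neither glucose nor ketones.
- Urine glucose and ketones are tested only at screening (8.8.3).
- Scheduled on-study glucose is measured only around the meal test, at Visits 1, 4 and 5 (8.16).
- Section 8.17.3 makes an abnormal laboratory value an adverse event if it has clinical manifestations, needs treatment or leads to discontinuation. With the measurements above, it cannot systematically detect episodes between visits.
- Section 8.17.4 requires all adverse events to be reported, whether or not drug-related. That takes effect only once an episode has been classed as an adverse event.

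**3. How long must a patient remember?** Visits 1 to 5 fall at months 0, 3, 6, 12 and 18. The nominal gaps are 3 − 0 = 3, 6 − 3 = 3, 12 − 6 = 6 and 18 − 12 = 6 months. The longest is 6 months, twice, and only a general question is asked at the end of it.

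**4. Is targeted questioning foreign to this protocol?** No. Section 5.3.2.1 asks three muscle questions in spite of the general rule in 8.17. Muscle symptoms are prompted for once and glycaemic episodes never.

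**The case against.** The strongest case on the other side has five parts.

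- *The filter is narrow.* A reader might infer that all diabetes events, hypoglycaemia included, count only if unexpected. The text does not support that: the filter concerns worsening symptoms of the treated condition, and it also admits an episode whose severity is unexpected. This stands. For hypoglycaemia the defect is unsettled classification and unstructured collection, not exclusion.
- *Safeguards exist.* Sections 8.17.2 to 8.17.4 have no expectedness test. This stands for serious episodes. It does not cover non-serious decompensation, and it leaves severe hypoglycaemia handled at home to judgment.
- *Bias between arms is not shown.* The trial is double-blind and each site has its own block of randomization numbers, so site habits should affect both arms alike. This stands.
- *The objectives are about atorvastatin, and both arms receive insulin.* Objective 2 is defined by HbA1c and insulin requirements. A reader might conclude that it cannot be interpreted without hypoglycaemia data. That goes too far: such data would add context, but the objective can be read without them.
- *Open questioning is a legitimate guard against suggestion, and tabulation belongs to the analysis plan.* Both stand. Section 9.6 provides that "The incidence of adverse events, drug-related adverse events and premature discontinuations will be summarized descriptively for each treatment group", and its lack of a separate hypoglycaemia table is not a fault. What cannot be left to the analysis plan is collecting the episodes in the first place.

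**Conclusion.** The point holds in a limited form. Section 8.17.1 does not settle how worsening diabetes and severe hypoglycaemia are to be recorded, the test it uses is undefined, and no visit procedure asks about either severe hypoglycaemia or ketoacidosis. The episodes exposed are non-serious decompensation and severe hypoglycaemia handled outside hospital. The expected effect is under-recording in both arms and variation between about 20 sites, which weakens a safety comparison that is only descriptive.

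The size cannot be given as a number of episodes. A reader might multiply the time under the target (for 160 completers, months 3 to 18: 160 × 15/12 = 200 patient-years) by an assumed rate of severe hypoglycaemia and call the result lost. The protocol supplies neither the rate nor the share of episodes that would go unrecorded, and severe episodes are the ones the filter touches least.

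The conclusion rests on two assumptions: investigators differ in what they regard as expected, and patients do not reliably volunteer past episodes to a general question. Both are plausible, but the document tests neither.

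**What to change.** 1. In 8.17.1, reconcile the three statements by saying that severe hypoglycaemia (help from another person needed) and ketoacidosis are always recorded as adverse events, regardless of expectedness.
2. Add one recorded question on whether either event has occurred since the last visit, at Visits 2 to 5 and at Early Discontinuation.
3. In 8.17, name this question as an exception to general questioning, together with the muscle questions in 5.3.2.1, so that those sections agree.

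Lesser hyperglycaemic symptoms would stay under investigator judgment, which is a defensible limit. Tabulation by arm can be left to the analysis plan.

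The cost is one CRF line at visits that already take place, and slightly more adverse-event entries. The change concerns recording only; it alters no dose, glycaemic target or rule of clinical care.

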8.17.2 Definition of Serious Adverse Events

Serious adverse event

A serious adverse event is defined as any untoward medical occurrence that:

- results in death
- is life- threatening (note: the term life threatening indicates that the patient was at immediate risk of death)
- results in inpatient hospitalization/ prolongation of hospitalization
- results in persistent or significant disability/incapacity
- results in a congenital anomaly or birth defect.

Important medical events that may not result in death, be life-threatening, or require hospitalization may be considered serious adverse drug events when, based upon appropriate medical judgment, they may jeopardize the subject and may require medical or surgical intervention to prevent one of the outcomes listed in this definition. Examples of such medical events include allergic bronchospasm requiring

intensive treatment in an emergency room or at home, blood dycrasias or convulsions that do not result in inpatient hospitalization, or the development of drug dependency or drug abuse.

Life-threatening means that the patient was, in the view of the investigator, at immediate risk of death from the reaction as it occurred. This does not include an adverse event that, had it occurred in a more serious form, might have caused death. Disability means a substantial disruption of a person's ability to conduct normal life's functions.

8.17.3 Change of Laboratory Parameters

Laboratory Test Variable as an Adverse Event

A laboratory test variable that is abnormal or has changed significantly since baseline should be recorded as an adverse event if it causes the patient to be discontinued from the study, there are clinical manifestations, or treatment is required.

8.17.4 Documentation and Reporting of Adverse Events

All adverse events occurring during the trial and follow-up period must be fully recorded in the patient's CRF.

The investigator or staff member must report all adverse events encountered during the clinical study, whether or not the event is considered drug-related.

The signs and symptoms of the individual adverse event must be described in detail: date of onset and end, intensity, relationship to the test drug, action taken and outcome.

Documentation must be supported by an entry in the patient's files.

The following data should be documented for each adverse event:

- Study code number.
- Patient identification number.
- Description of the symptom/event.
- · Classification of "serious" or "not serious".
- Intensity.
- Date of first and last occurrence.
- Frequency (once, occasionally, frequently, permanently).
- Treatment required (no treatment necessary, treatment with prescription only drug(s), outpatient treatment (with dates recorded), inpatient treatment (hospitalization), prolonged hospitalization (with dates recorded).
- Causal relationship to investigational product(s) (according to CPMP guideline III/3445/91).
- Outcome of event (unknown, recovered, not yet recovered, sequelae with disability/incapacity, death (with date and cause recorded).

Any adverse event (serious or otherwise), that could affect adversely the safety of patients or the conduct of the trial should be reported to Profil by telephone and/or fax within 24 hours using the adverse event expedited reporting form provided. Profil will inform Pfizer Deutschland GmbH within 24 hours after the event has been reported.

The information must comprise at least the following data:

- Name, address and telephone number of the reporting investigator.
- Investigational product.
- Study code.
- Patient identification number, initials, sex and date of birth.
- Description of the adverse event, measures taken and outcome.
- Preliminary classification of causal relationship by the investigator according to CPMP guideline III/3445/91

This information can be transmitted via telephone or fax.

On behalf of Pfizer Deutschland GmbH, Profil will promptly notify all relevant investigator(s)/institution(s) and the regulatory authority(ies) of findings that could affect adversely the safety of patients, impact on the conduct of the trial, or alter the ethics committee approval/favorable opinion of the trial. In addition, Profil will expedite the reporting to all concerned investigator(s)/institutions(s), to the ethics committees, where required, and to the regulatory authority(ies) of all adverse events that are both serious and unexpected.

9 STATISTICAL EVALUATION

9.1 Determination of sample size

For the primary endpoint the calculation of sample size is based on data on levels and variation taken from a recent study at the German Diabetes Clinic. After 12 months of intense insulin treatment, stimulated C-peptide was 0.37 ± 0.053 nmol/l (mean \pm standard deviation) With a sample size of 80 patients per group a 20% difference in stimulated C-peptide would be significant with a p-value < 0.01.

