 To assess the effect on systemic immune abnormalities in patients with type 1 diabetes mellitus as measured by effects on beta-cell autoantibodies, blood cytokines and chemokines on protein and transcriptional level

Number of patients: Up to 160 patients with recent onset type 1 diabetes

mellitus should complete all study procedures. Patients who are withdrawn from the study during the first nine

months of treatment will be replaced.

Number of study sites: About 20 study sites will participate in this trial. The

number of sites may be adjusted to assure a sufficient

number of patients can be included.

The German Diabetes Clinic will participate with

approximately 25 to 35 patients.

DIATOR

Protocol Version 2.3 07/01/2004

Efficacy endpoints:

Primary efficacy endpoint:

 Area under the C-peptide curve in a 2 hour mixed meal tolerance test after 12 months and 18 months of treatment

Secondary efficacy endpoint:

HbA1c and insulin requirements after 12 and 18 months of treatment

Study drug regimen:

starting dose 40 mg/day for 4 weeks, then increase to 80 mg/day, in case of side effects reduction to 40 mg/day

Frequency: daily, as recommended

Route: oral

Duration: 18 months

Table of contents

1	LIST	of Addreviations	8
2	lovo	estigators and Study Administrative Structure	10
_	2.1	Requirements of the Investigator(s) and Study Sites	
	2.2	Administrative Structure	10
	۷.۲	Administrative offactore	
3	Intro	oduction	12
_			
4	Stuc	dy Objectives	14
5		rall Study Design and Procedures	
	5.1	Study Design	
	5.2	Study Flow Chart	
	5.3	Study Procedures	
	5.3.		
	5.3.		
	5.3.		
	5.3.4		
	5.3.		
	5.3.0 5.3.1		
	5.5.	7 Early Discontinuation Visit	21
6	Sele	ection of Study Population	22
_	6.1	Primary Diagnosis	
	6.2	Number of Subjects	
	6.3	Inclusion Criteria	
	6.4	Exclusion Criteria	
	6.5	Withdrawal Criteria	23
7		atments to be Administered	
	7.1	Identity of Investigational Product	
	7.2	Labeling and Packaging of the Investigational Product	
	7.3	Drug Accountability	
	7.4	Blinding	
	7.5	Randomization	
	7.6	Treatment Compliance	20
8	Stuc	dy Assessments	27
_	8.1	Demographic Data	
	8.2	Medical History, including Concomitant Illnesses	
	8.3	Concomitant Medication, including insulin requirements	
	8.4	Body weight, Height and BMI	
	8.5	Vital Signs	
	8.6	Physical Examination	28
	8.7	12-Lead ECG	
	8.8	Safety Laboratory	
	8.8.	0,	
	8.8.	2 Clinical chemistry	28

8.	.8.3	Urinalysis	
8.	.8.4	Coagulation	
8.9		rum Lipids	
8.10		gnancy Test	

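### Section 9.1 does not support 80 per group: its stated inputs need about 14 to 18, no power is given, and the variable is not the primary endpoint

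*Protocol*

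**What the plan says.** Section 9.1 says that the calculation serves the primary endpoint and is "based on data on levels and variation taken from a recent study at the German Diabetes Clinic". The inputs are a 12-month value under intense insulin treatment, "stimulated C-peptide was 0.37 ± 0.053 nmol/l", which the text labels mean ± standard deviation. The conclusion follows at once: "With a sample size of 80 patients per group a 20% difference in stimulated C-peptide would be significant with a p-value < 0.01". Section 9.1 states no power, sidedness or test, and does not give the size of the source study.

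The Synopsis defines the primary efficacy endpoint as "Area under the C-peptide curve in a 2 hour mixed meal tolerance test after 12 months and 18 months of treatment". Section 6.2 sets a maximum of 160 completers, randomised one-to-one, and allows the number to change after the interim analysis in section 9.9.

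**The concern.** A sample-size paragraph should let the reader get from the inputs to the number. Here the stated SD is only 14% of the mean (0.053/0.37), and the difference of interest is well over one SD. Such inputs normally lead to a very small trial, yet the protocol arrives at 80 per group. Either the size was set on grounds that 9.1 does not state, or one of the inputs is not what its label says.

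Section 9.1 is the only justification given for 160 patients. If the SD is right, the trial is several times larger than its stated aim requires. If the SD is too small, the trial may be less sensitive to a 20% difference than the reader is led to believe. Section 9.1 does not let the reader tell which case applies.

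**Working it through.** **Inputs (section 9.1).** Mean 0.37 nmol/l; SD 0.053 nmol/l; difference 20%; p < 0.01; 80 per group. Allocation is 1:1 (section 6.2). Sidedness and power are not stated, so two-sided tests and 80–90% power are assumed.

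**1. The plan's own statement.**
- Difference: 0.20 × 0.37 = 0.074 nmol/l. Standardised: 0.074/0.053 = 1.40.
- Standard error of the difference with 80 per group: 0.053 × √(2/80) = 0.00838.
- t = 0.074/0.00838 = 8.83 on 158 degrees of freedom, p ≈ 2 × 10⁻¹⁵.

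This is below 0.01, so the sentence is true, by a very wide margin.

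**2. The size that these inputs require** (two-sample t-test, noncentral t, smallest n per group that reaches the power).

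| Two-sided alpha | 80% power | 90% power |
|---|---|---|
| 0.01 | 14 | 18 |
| 0.05 | 10 | 12 |

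At alpha 0.01, 80 is 80/18 = 4.4 to 80/14 = 5.7 times the required size. The normal approximation was also run one- and two-sided, at both alphas, with power from 80% to 99%. Its largest result is 25 per group, so no variant comes near 80.

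**3. What 80 per group delivers if SD = 0.053.**
- Power for a true 20% difference at alpha 0.01: above 99.9%.
- Smallest observed difference with p < 0.01: 2.607 × 0.00838 = 0.0218 nmol/l, or 5.9% of 0.37.
- Difference detectable at alpha 0.01 (normal approximation): (2.576 + 0.842) × 0.00838 = 0.0286 nmol/l, or 7.7%, with 80% power; (2.576 + 1.282) × 0.00838 = 0.0323 nmol/l, or 8.7%, with 90% power.

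**4. The SDs that fit 80 per group and a 20% difference.**
- Largest SD at which an observed 20% difference still gives p < 0.01: 0.074/(2.607 × √(2/80)) = 0.180. At that SD, power against a true 20% difference is only about 50% at alpha 0.01 and 74% at alpha 0.05.
- SD at which 80 is the required size at alpha 0.01 (normal approximation): 0.074 × √40/(2.576 + 0.842) = 0.137 for 80% power; 0.074 × √40/(2.576 + 1.282) = 0.121 for 90%.

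These SDs are 2.3 to 3.4 times the stated one.

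**5. If 0.053 were a standard error.** Then SD = 0.053 × √m, where m is the size of the source study. The protocol does not give m, so the values below are assumptions. Power is for a true 20% difference with 80 per group (noncentral t).

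| m (assumed) | SD | Power, alpha 0.01 | Power, alpha 0.05 |
|---|---|---|---|
| 5 | 0.119 | 91% | 98% |
| 10 | 0.168 | 57% | 79% |
| 20 | 0.237 | 27% | 50% |
| 40 | 0.335 | 12% | 28% |

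**6. The variable.** The input is a stimulated concentration in nmol/l at 12 months. The primary endpoint is an AUC at 12 and 18 months. Section 9.1 gives no SD for the AUC and no figure for month 18.

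**The case against.** The strongest reply is that nothing in 9.1 is false. "would be significant with a p-value < 0.01" is an inequality, and an SD of 0.053 satisfies it easily. The text calls 0.053 a standard deviation, and on the printed figures the trial has more power than it needs. This stands. A reader might infer that the paragraph contradicts itself, or that 0.053 cannot be an SD. The document supports neither. The value 0.18 is only the largest SD for which the sentence holds.

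A reader might also infer that the trial is underpowered. That requires 0.053 to be too small, for instance a mislabelled standard error. Under the standard-error reading, the source study must also have been large enough: with m = 5, power is still 91% at alpha 0.01. The document establishes neither condition.

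Second, section 9.9 allows the sample size to be adjusted at the interim analysis, so a wrong planning SD could come to light there. That is a possible later correction. It does not repair the basis stated now.

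Third, the Introduction itself describes beta-cell function as determined by stimulated C-peptide levels, and nothing shows that the AUC has a materially different relative spread. That is fair, and the effect of the endpoint mismatch cannot be quantified. It remains true that 9.1 claims to serve the primary endpoint and uses a different variable, at only one of the two time points.

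**Conclusion.** The point holds as a fault in the stated justification. With the printed mean, SD and difference, 14 to 18 per group suffice for 80–90% power at two-sided alpha 0.01, so 80 is about 4.4 to 5.7 times what the inputs require. This rests on a two-sample t-test with 1:1 allocation; other conventional choices of alpha, sidedness and power do not close the gap. Independently of the SD, 9.1 gives no power and describes the significance of an observed difference. Its input is also not the primary endpoint.

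That 0.053 is a standard error is a plausible explanation of the gap and no more than that. The power figures under that reading run from 91% down to 12% at alpha 0.01 as the assumed m goes from 5 to 40. They show why the label must be checked and are not an estimate of this trial's power. The paragraph should be corrected, because the trial's size rests on it alone.

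**What to change.** Go back to the clinic's source data and establish whether 0.053 is an SD or a standard error, and from how many patients. Then rewrite section 9.1 with:
- the verified SD of the C-peptide AUC, the primary endpoint, with the time point that the calculation serves;
- a two-sided alpha and a stated power;
- if 80 per group is kept, the difference detectable with 80% or 90% power, in place of the statement that a 20% difference would be significant.

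The cost is one paragraph of protocol text and a look at existing data. It needs no additional patients. The downside is that the stated detectable difference may become less favourable than 20%.
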